3.3.5.2 Rationale for the Collection of Tissue Samples

Archival or fresh tumor tissue (preferred) will be collected. A specimen from the most recently obtained tumor tissue will be requested to obtain the most accurate reflection of a patient's current disease, while minimizing burden. Tumor tissues may be assessed for ER, progesterone receptor, and HER2 protein levels, and proliferative index (Ki67). In addition, tumor tissue may enable assessment of ER pathway activity using RNA analysis of ER target genes (Guan et al. 2019). NGS techniques such as targeted exome sequencing may offer a unique opportunity to identify biomarkers of response and/or resistance to GDC-9545 in tumor tissue. For example, genes related to PI3K signaling and endocrine resistance as well as reported and unreported chromosomal alterations resulting from the tumorigenesis process may be assessed. Mutations in the *ESR1* gene are more prevalent in metastatic ER-positive tumors and have been correlated with resistance to anti-estrogen therapies (Robinson et al. 2013; Toy et al. 2013; Jeselsohn et al. 2014). Tumor tissue analysis offers the opportunity to perform molecular subtyping that may inform breast cancer biology and response to GDC-9545 or endocrine therapy. The collection of tissue samples may also support future diagnostic development.

Tissue samples will be collected for DNA extraction to enable whole genome sequencing (WGS) or whole exome sequencing (WES) to identify variants that are predictive of response to study drug, are associated with progression to a more severe disease state, are associated with acquired resistance to study drug, are associated with susceptibility to developing adverse events, can lead to improved adverse event monitoring or investigation, or can increase the knowledge and understanding of disease biology and drug safety. Genomics is increasingly informing researchers' understanding of disease pathobiology. WGS and WES provide a comprehensive characterization of the genome and exome, respectively, and, along with clinical data collected in this study, may increase the opportunity for developing new therapeutic approaches or new methods for monitoring efficacy and safety or predicting which patients are more likely to respond to a drug or develop adverse events. Data will be analyzed in the context of this study but may also be explored in aggregate with data from

other studies. The availability of a larger dataset will assist in identification and characterization of important biomarkers and pathways to support future drug development.

3.3.6 Rationale for Clinical Outcome Assessments

As metastatic breast cancer is not curable with currently approved and available therapies, the primary focus for patients is prolonging life and delaying the progression of cancer, while maintaining quality of life and the ability to carry out daily activities (Cardoso et al. 2012). Research indicates that a higher proportion of HR-positive patients have bone metastases compared with other subtypes, which is often associated with pain (Irvin et al. 2011; Wood et al. 2016); thus, disease-related pain may be an important variable to assess during treatment. Limited data are available characterizing the clinical presentation of disease in this population; however, it is hypothesized that progression of disease would be associated with an increase in pain symptoms. Hence, examining and measuring patients' disease-related pain and interference with functioning is important.

Additionally, cancer treatments, particularly combination therapies, can produce significant symptomatic adverse events. Recent research has shown that clinicians may underreport the incidence and severity of symptoms experienced by patients receiving treatment for cancer (Fromme et al. 2004; Trotti et al. 2007; Pakhomov et al. 2008; Basch 2010; Quinten et al. 2011; Atkinson et al. 2012; Basch et al. 2014). Collecting tolerability information directly from patients can provide a better understanding of treatment characteristics and their effects.

These issues will be assessed using validated PRO assessments in patients enrolled in the study. The QLQ-C30 will be administered to patients to assess disease and treatment-related symptoms, functioning, and GHS/QoL. The QLQ-BR23 will provide an additional assessment of some treatment-related symptoms and symptoms that may occur with advanced disease. The "worst pain" item from the BPI-SF will be used to gain further insight into increase in pain severity. For evaluation of the tolerability of GDC-9545, patients will be asked to report on their experience related to diarrhea, nausea, vomiting, decreased appetite, fatigue, mouth sores, and rash selected from the validated PRO-CTCAE item bank. These symptoms were identified as being salient to patients' experience with GDC-9545 and/or common endocrine therapies on the basis of preliminary and published safety data, respectively. An additional exploratory safety endpoint has been specified to evaluate the overall treatment burden patients may experience, which will be assessed by analyzing the proportion of patients who select each response option at each assessment timepoint by treatment arm for the single-item GP5 ("I am bothered by side effects of treatment") from the Physical Well-Being subscale of the validated and reliable FACT-G instrument,

Version 4 (Cella et al. 1993; Webster et al. 1999). The EQ-5D-5L will also be collected and utilized to derive health states for use in economic models; therefore, the results will not be reported in the Clinical Study Report. See Section 4.5.9 and [Appendix 5–Appendix 10](#) for additional details on PRO instruments used in this study.

The PRO data collected in the study will be supplemented by (optional) interviews conducted among a subset (up to 30) of patients treated with GDC-9545 to further understand the experiences of study treatment, therapeutic context, and disease journey from the patient perspective.

4. MATERIALS AND METHODS

4.1 PATIENTS

Approximately 300 patients with ER-positive, HER2-negative locally advanced or metastatic breast cancer who have received one or two prior lines of systemic therapy in the locally advanced or metastatic setting will be enrolled during the global enrollment phase of this study. After completion of the global enrollment phase, additional patients may be enrolled in an extended China enrollment phase.

4.1.1 Inclusion Criteria

Patients must meet the following criteria for study entry:

- Signed Informed Consent Form
- Age ≥ 18 years at time of signing Informed Consent Form
- For women: postmenopausal or premenopausal/perimenopausal status, defined as follows:

Postmenopausal, as defined by at least one of the following criteria:

- Age ≥ 60 years
- Age < 60 years and ≥ 12 months of amenorrhea without an alternative medical cause plus follicle-stimulating hormone (FSH) and plasma estradiol levels within postmenopausal range by local laboratory assessment, in the absence of oral contraceptive pills, hormone replacement therapy, or gonadotropin-releasing hormone agonist or antagonist.
- Documented bilateral oophorectomy (≥ 14 days prior to first treatment on Day 1 of Cycle 1 and recovery from surgery to baseline)

Premenopausal or perimenopausal, defined as not meeting the criteria for postmenopausal, and willing to undergo and maintain treatment with approved LHRH-agonist therapy for the duration of study treatment

LHRH-agonist therapy may be initiated 28 days prior to Day 1 of Cycle 1 (or according to clinical practice for the selected agent). To

minimize the potential of exposure to the medication decreasing to sub-therapeutic levels towards the end of the treatment cycle, monthly injections of LHRH agonist are preferred and to be synchronized with Day 1 of each 28-day cycle.

- For men: willing to undergo and maintain treatment with approved LHRH-agonist therapy for the duration of study treatment
- Locally advanced or metastatic adenocarcinoma of the breast, not amenable to treatment with curative intent
- Disease progression after treatment with one or two lines of systemic therapy in the locally advanced or metastatic setting

LHRH-agonist therapy may be initiated 28 days prior to Day 1 of Cycle 1 (or according to clinical practice for the selected agent). To minimize the potential of exposure to the medication decreasing to sub-therapeutic levels towards the end of the treatment cycle, monthly injections of LHRH agonist are preferred and to be synchronized with Day 1 of each 28-day cycle.

One of the prior lines of systemic therapy may have included chemotherapy.

Patients may not have received more than one prior targeted therapy regimen in the locally advanced or metastatic setting. Targeted therapies may include, but are not limited to, CDK4/6 inhibitors, mTOR inhibitors, PI3K inhibitors or PARP inhibitors.

One of the prior lines of systemic therapy must have included endocrine therapy, which must have been administered continuously for a minimum of 6 months in the locally advanced or metastatic setting prior to disease progression.

Patients who were intolerant to their last systemic anti-cancer regimen may be considered eligible if all other eligibility criteria are met (including a minimum of 6 months continuous endocrine therapy).

Intolerance is defined as any treatment-related Grade 4 adverse event, or any treatment-related Grade 2 or 3 adverse event that is unacceptable to the patient and persists despite standard countermeasures. The reason for intolerance must be fully documented.

- Documented ER-positive tumor according to American Society of Clinical Oncology/College of American Pathologists (ASCO/CAP) or ESMO guidelines, assessed locally and defined as $\geq 1\%$ of tumor cells stained positive based on the most recent tumor biopsy (or archived tumor sample)
Patient must be considered appropriate for endocrine therapy.
- Documented HER2-negative tumor assessed locally and defined as meeting criteria according to ASCO/CAP guidelines (Wolff et al. 2018).

- Confirmed availability of the most recently collected and representative tumor tissue specimen suitable for biomarker testing with de-identified associated pathology report is required (i.e., archived formalin-fixed, paraffin-embedded [FFPE] tissue block [preferred] or 15–20 slides containing unstained, freshly cut, serial sections). Whenever possible, tumor tissue from a metastatic site of disease is preferred, but archival tumor tissue from the primary tumor is acceptable if it is the most recently collected or most suitable for testing (see Section 4.5.7 and the laboratory manual)

If tumor tissue is not available, a newly collected, pre-treatment biopsy will be required for patient participation. In general, a minimum of three cores per block is preferred.

If the aforementioned minimum tissue requirements cannot be met because of local regulatory requirements, patient may still be eligible for the study and study team is available for advice.

- Measurable disease as defined per RECIST v.1.1 or bone only disease which must have at least one predominantly lytic bone lesion confirmed by CT or MRI which can be followed.

Tumor lesions previously irradiated or subjected to other locoregional therapy will be deemed measurable only if disease progression at the treated site after completion of therapy is clearly documented.

- Eastern Cooperative Oncology Group (ECOG) Performance Status 0–1
- Life expectancy of >6 months
- Adequate organ function as defined by the following criteria:

- ANC $\geq 1.5 \times 10^9/L$ (1500/ μ L)
- Platelet count $\geq 100 \times 10^9/L$ (100,000/ μ L)
- AST and serum ALT $\leq 3 \times$ upper limit of normal (ULN)

For patients with documented liver metastasis: AST and ALT $\leq 5 \times$ ULN

- Hemoglobin ≥ 90 g/L (9 g/dL)

The blood counts are to meet the specified criteria without transfusion or growth factor support, unless it is clear that the bone marrow function is adequate and that any aberration has a clear and correctable cause, and the correction undertaken.

- Serum bilirubin $\leq 1.5 \times$ ULN, with the following exception:

Patients with known Gilbert syndrome: $\leq 3 \times$ ULN

- Serum creatinine $\leq 1.5 \times$ ULN or estimated creatinine clearance ≥ 60 mL/min as calculated per institutional guidelines

- INR (or PT) $< 1.5 \times$ ULN and PTT (or aPTT) $< 1.5 \times$ ULN (except for patients receiving anticoagulation therapy)

For patients receiving warfarin, a stable INR between 2 and 3 is required.

For patients receiving heparin, PTT (or aPTT) between 1.5 and 2.5× ULN (or patient's value before starting heparin treatment) is required.

If anticoagulation therapy is required for a prosthetic heart valve, stable INR between 2.5 and 3.5 is permitted.

- Resolution of all acute toxic effects of prior anti-cancer therapy or surgical procedures to NCI CTCAE v5.0 Grade ≤ 1 (except alopecia, Grade ≤ 2 peripheral neuropathy, or other toxicities not considered a safety risk for the patient per investigator's judgment)
- For women of childbearing potential: agreement to take precautions as outlined below for each treatment arm
 - If assigned to the control arm (physician's choice of endocrine monotherapy), agreement to comply with local prescribing guidelines regarding contraception for the chosen endocrine monotherapy
 - If assigned to the GDC-9545 arm: agreement to remain abstinent (refrain from heterosexual intercourse) or use contraception, and agreement to refrain from donating eggs, as defined below:

Women must remain abstinent or use non-hormonal contraceptive methods with a failure rate of < 1% per year during the treatment period and for 10 days after the final dose of GDC-9545 or for the time period according to local prescribing guidelines. Women must refrain from donating eggs during this same period.

A woman is considered to be of childbearing potential if she is postmenarchal, has not reached a postmenopausal state (≥ 12 continuous months of amenorrhea with no identified cause other than menopause), and is not permanently infertile due to surgery (i.e., removal of ovaries, fallopian tubes, and/or uterus) or another cause as determined by the investigator (e.g., Müllerian agenesis). The definition of childbearing potential may be adapted for alignment with local guidelines or regulations.

Examples of non-hormonal contraceptive methods with a failure rate of < 1% per year include bilateral tubal ligation, male sterilization, and copper intrauterine devices.

For women of childbearing potential, hormonal contraceptive methods are not allowed in this study.

The reliability of sexual abstinence should be evaluated in relation to the duration of the clinical trial and the preferred and usual lifestyle of the patient. Periodic abstinence (e.g., calendar, ovulation, symptothermal, or postovulation methods) and withdrawal are not adequate methods of contraception. LHRH agonists are not adequate contraception. If required per local guidelines or regulations, locally recognized adequate methods of contraception and information about the reliability of abstinence will be described in the local Informed Consent Form.

- For men: agreement to take precautions as outlined below for each treatment arm:
 - If assigned to the control arm (physician's choice of endocrine monotherapy), agreement to comply with local prescribing guidelines regarding contraception for the chosen endocrine monotherapy
 - If assigned to the GDC-9545 arm: agreement to remain abstinent (refrain from heterosexual intercourse) or use contraceptive methods, and agreement to refrain from donating sperm, as defined below:

With a female partner of childbearing potential who is not pregnant, men must remain abstinent or use a condom plus an additional contraceptive method that together result in a failure rate of < 1% per year during the treatment period and for 10 days after the final dose of GDC-9545 or for the time period according to local prescribing guidelines. Men must refrain from donating sperm during this same period.

With a pregnant female partner, men must remain abstinent or use a condom during the treatment period and for 10 days after the final dose of GDC-9545 or for the time period according to local prescribing guidelines to avoid exposing the embryo. Men must refrain from donating sperm during this same period.

The reliability of sexual abstinence should be evaluated in relation to the duration of the clinical trial and the preferred and usual lifestyle of the patient. Periodic abstinence (e.g., calendar, ovulation, symptothermal, or postovulation methods) and withdrawal are not adequate methods of contraception. If required per local guidelines or regulations, locally recognized adequate methods of contraception and information about the reliability of abstinence will be described in the local Informed Consent Form.

For female partners of male patients, hormonal contraceptive methods supplemented by a barrier method are permitted.

- Ability to comply with the study protocol, in the investigator's judgment
- Willing and able to use an electronic device for PRO data collection

- For patients enrolled in an extended China enrollment phase: current resident of mainland China, Hong Kong, or Taiwan, and of Chinese ancestry

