- Age ≥ 18 years at time of signing Informed Consent Form
- For women: postmenopausal or premenopausal/perimenopausal status, defined as follows:

Postmenopausal, as defined by at least one of the following criteria:

- Age ≥ 60 years
- Age < 60 years and ≥ 12 months of amenorrhea **without an alternative medical cause** plus follicle-stimulating hormone and plasma estradiol levels within postmenopausal range by local laboratory assessment, in the absence of oral contraceptive pills, hormone replacement therapy, or gonadotropin-releasing hormone agonist or antagonist.
- Documented bilateral oophorectomy (≥ 14 days prior to first treatment on Day 1 of Cycle 1 and recovery from surgery to baseline)

Premenopausal or perimenopausal, defined as not meeting the criteria for postmenopausal, and willing to undergo and maintain treatment with approved LHRH-agonist therapy for the duration of study treatment

LHRH-agonist therapy may be initiated 28 days prior to Day 1 of Cycle 1 (or according to clinical practice for the selected agent). To minimize the potential of exposure to the medication decreasing to sub-therapeutic levels towards the end of the treatment cycle, monthly injections of LHRH agonist are preferred and to be synchronized with Day 1 of each 28-day cycle.

- For men: willing to undergo and maintain treatment with approved LHRH-agonist therapy for the duration of study treatment

LHRH-agonist therapy may be initiated 28 days prior to Day 1 of Cycle 1 (or according to clinical practice for the selected agent). To minimize the potential of exposure to the medication decreasing to sub-therapeutic levels towards the end

of the treatment cycle, monthly injections of LHRH agonist are preferred and to be synchronized with Day 1 of each 28-day cycle.

- Locally advanced or metastatic adenocarcinoma of the breast, not amenable to treatment with curative intent
- Disease progression after treatment with one or two lines of systemic therapy in the locally advanced or metastatic setting

One of the prior lines of systemic therapy may have included chemotherapy.

Patients may not have received more than one prior targeted therapy regimen in the locally advanced or metastatic setting. Targeted therapies may include, but are not limited to CDK4/6 inhibitors, mTOR inhibitors, PI3K inhibitors or PARP inhibitors.

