For patients who have been successfully treated for viral hepatitis, the possibility of re-activation of the virus or reinfection with viral hepatitis should

be considered by the Investigator and the overall potential benefits associated with study treatment for the patient should be deemed to exceed the overall risks.

- Known HIV infection
- Active inflammatory bowel disease, chronic diarrhea, short bowel syndrome, or major upper gastrointestinal (GI) surgery, including gastric resection, potentially affecting enteral absorption
- Serious infection requiring oral or IV antibiotics, or other clinically significant infection, within 14 days prior to randomization. Patients who fully recovered from serious and clinically significant infections within 14 days prior to randomization are eligible.
- Any serious medical condition or abnormality in clinical laboratory tests that, in the investigator's judgment, precludes the patient's safe participation in and completion of the study
- Known allergy or hypersensitivity to any of the study drugs or any of their excipients
- For premenopausal/perimenopausal patients or male patients: known hypersensitivity to LHRH agonists
- Pregnant or breastfeeding, or intending to become pregnant during the study or within 10 days after the final dose of GDC-9545, or within the time period specified per local prescribing guidelines after the final dose of physician's choice of endocrine monotherapy

Women of childbearing potential must have a negative serum pregnancy test result within 7 days prior to initiation of study treatment.

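### Protocol Section 4.1.1 and the synopsis each hold two definitions of postmenopausal; read literally, one narrow group of women on an LHRH agonist has no contraception or pregnancy-test requirement

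*Protocol*

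**What the plan says.** **Menopausal status (Protocol Section 4.1.1).** A woman under 60 without bilateral oophorectomy counts as postmenopausal only if she has at least 12 months of amenorrhea with no other medical explanation, "plus follicle-stimulating hormone (FSH) and plasma estradiol levels within postmenopausal range by local laboratory assessment". Everyone else falls into the residual class: "Premenopausal or perimenopausal, defined as not meeting the criteria for postmenopausal". Women in that class receive an LHRH agonist. The synopsis has the same hormone condition: "plus follicle-stimulating hormone and plasma estradiol levels within postmenopausal range by local laboratory assessment".

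**Childbearing potential (same section, later bullet).** A postmenarchal woman who is not permanently infertile is of childbearing potential if she "has not reached a postmenopausal state (≥ 12 continuous months of amenorrhea with no identified cause other than menopause". No FSH or estradiol condition appears. The synopsis repeats this. The bullet adds that "The definition of childbearing potential may be adapted for alignment with local guidelines or regulations" and that "LHRH agonists are not adequate contraception".

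**What hangs on childbearing potential.** The contraception agreement in Section 4.1.1 is addressed to these women. For the control arm it is an "agreement to comply with local prescribing guidelines regarding contraception for the chosen endocrine monotherapy"; for GDC-9545 it is abstinence or effective non-hormonal contraception during treatment and for 10 days afterwards. Section 4.1.2 says "Women of childbearing potential must have a negative serum pregnancy test result within 7 days prior to initiation of study treatment". Section 4.5.7 and Appendix 1 (footnote n) schedule the serum and urine tests for the same women.

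**The concern.** The two definitions serve different purposes and need not be identical. In one case, however, the definition that protects a fetus is less cautious than the one that decides on ovarian suppression. The protocol would treat a woman's ovaries as functioning, suppress them with an LHRH agonist and monitor her hormones, while not asking her for contraception or pregnancy tests. The protocol itself says that the LHRH agonist does not fill that role.

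The stake is fetal exposure. Section 5.1.2.5 expects an adverse effect of GDC-9545 in pregnancy, with birth defects and miscarriage named. This is a participant-safety and wording point. It has no bearing on PFS or any other efficacy analysis.

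**Working it through.** The plan gives no figure on this point, so the check applies the two definitions to one case and then asks which rules reach her.

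**The case.** A postmenarchal woman under 60, with no oophorectomy and not permanently infertile, has at least 12 continuous months of amenorrhea. Nothing but menopause has been identified as its cause. FSH or estradiol is outside the postmenopausal range.

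1. *Menopausal status.* She fails the age and oophorectomy criteria, and the remaining criterion fails on hormones. She is pre/perimenopausal and receives an LHRH agonist.
2. *Childbearing potential.* On amenorrhea alone she has reached a postmenopausal state. She is not of childbearing potential.
3. *Synopsis.* It contains the same two definitions and gives the same result.

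**Who is not in the gap.** Women aged 60 or over are postmenopausal by age. A woman whose amenorrhea is attributed to chemotherapy or to an LHRH agonist has another identified cause, so she remains of childbearing potential. In this pretreated population that removes many of the likely candidates.

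**Which rules reach her, read literally**

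| Rule | Protocol location | Reaches her? |
|---|---|---|
| Contraception agreement | 4.1.1 | No |
| Serum test at entry | 4.1.2, 4.5.7 | No |
| Scheduled urine tests | 4.5.7, Appendix 1 footnote n | No |
| Exclusion for pregnancy or intended pregnancy | 4.1.2 | Yes |
| Ban on hormonal contraceptives | 4.4.3 | Yes |
| Permanent discontinuation on pregnancy | 4.6.1 | Yes |
| Investigator reports pregnancy within 24 hours | 5.4 | Yes |
| FSH/estradiol on Day 1 of Cycles 1–3, then every three cycles | Appendix 1 footnote m | Yes |

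The first three rules prevent or detect a pregnancy. The next four exclude or respond to one, or restrict the choice of contraceptive without requiring any. The last is continuing surveillance of ovarian function, but it is neither contraception nor a pregnancy test.

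**Rough ceiling on the group.** Inputs: 303 enrolled (Section 1.2.2.2), 1:1 allocation, and pre/perimenopausal plus male patients limited to about 20% (Section 3.1.1).

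- Capped group: 303 × 0.20 = 60.6.
- GDC-9545 arm, assuming an even split: 60.6 / 2 = 30.3, about 30.
- Menopausal status is not a stratification factor, so the split can vary by chance: √(60.6 × 0.25) = 3.9, and 30.3 ± 1.96 × 3.9 is about 23 to 38.

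This is a ceiling before removing men, ordinary premenopausal women, treatment-induced amenorrhea and patients off treatment. At the February 2022 cutoff most patients remaining in the study had already stopped treatment (Section 1.2.2.2).

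**Burden of closing the gap.** One urine test per 28-day cycle is 365.25 / 28 = 13.04, about 13 per year, plus 1 at the discontinuation visit. The remaining treatment time is an assumption: 3 cycles give 3 + 1 = 4 tests, 6 give 6 + 1 = 7, and 13 give 13 + 1 = 14. The entry serum test is not counted because enrollment is complete.

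**The case against.** The best reply is that no sensible investigator would open this gap. FSH and estradiol are measured at screening in women under 60. The investigator would have to see non-postmenopausal results, class her as pre/perimenopausal, start an LHRH agonist, and still record that menopause explains her amenorrhea. The remark that LHRH agonists are not adequate contraception also sits inside the childbearing-potential bullet. Among women, only pre/perimenopausal patients receive these drugs, so the authors evidently expected such women to fall under the contraception rules. Local adaptation is allowed as well.

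Much of this stands. It makes the gap unlikely in practice and shows what was intended. It does not close the gap. No text links the two definitions, abnormal hormone results do not in themselves identify another cause, and local adaptation is permitted but not required.

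Three stronger readings are tempting, and the documents do not support them.

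- *Premenopausal women in general escape contraception.* They do not. The gap needs 12 months of amenorrhea with menopause as its only identified cause.
- *Section 4.1.1 and the synopsis contradict each other.* They agree; the mismatch lies within each.
- *The consent form fails to tell her to report a pregnancy.* Section 5.4.3.1 says what the form will tell women of childbearing potential. The form itself is not among the documents reviewed and may instruct all women.

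**Conclusion.** The mismatch is real but narrow. On a literal reading, a woman can be pre/perimenopausal and on an LHRH agonist without being required to use contraception or have scheduled pregnancy tests. The documents do not count such women. They are a small part of the roughly 30 capped patients in the GDC-9545 arm, and there may be none. The figure of 30 assumes that the cap was filled and split evenly between arms.

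Because enrollment is complete, the point concerns only women still on GDC-9545 or within 10 days of the final dose. Other pregnancy rules and hormone monitoring still apply to them. It is an optional, cheap safety clarification rather than a defect in the trial's conduct or inference. Confidence is moderate, since the practical effect depends on how investigators apply the wording.

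**What to change.** Add one sentence to the childbearing-potential definition in Section 4.1.1 and in the synopsis: *Any woman classed as premenopausal or perimenopausal under Section 4.1.1 is considered of childbearing potential unless permanently infertile.* State that it applies to women still on GDC-9545 or within 10 days of the final dose, and that control-arm contraception stays under local prescribing guidelines.

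The menopausal-status definition stays as it is, so the SAP's subgroup by menopausal status (Section 5.3.5.1) does not change. No new data are needed to identify affected women, because FSH and estradiol are already collected in women under 60 (Section 4.5.7). A late edit of this kind is practical: the Version 4 amendment summary records that the contraception text was updated for embryo-fetal toxicity although enrollment had closed.

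The cost is the wording change plus, for any affected woman, a contraception agreement and the urine tests counted above.
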